#### 5.1.2 Nivolumab

Nivolumab is approved in all of the participating countries (South Korea, Taiwan and the UK) for oncologic indications. It is provided as a 10 mg/mL solution in a glass vial with a coated butyl rubber stopper and sealed with an aluminium cap.

## 5.2 Investigational Products Administered

The IMPs to be given in each treatment group are shown in [Table 1](#). Groups 1 and 4 are closed to further randomization. Groups 2 and 3 will continue to recruit approximately 16 participants in a 1:1 ratio.

**Table 1 Study Vaccine Treatment Groups in HBV002**

Treatment Group	Study Vaccine Day 0	Study Vaccine Day 28
Group 1 (N=10)	MVA 1 x 10  pfu	MVA 1 x 10  pfu
Group 2 (N=16)	ChAdOx1-HBV 2.5 x 10  vp	MVA 1 x 10  pfu
Group 3 (N=16)	ChAdOx1-HBV 2.5 x 10  vp	MVA 1 x 10  pfu + nivolumab 0.3 mg/kg
Group 4 (N=8-10)	ChAdOx1-HBV 2.5 x 10  vp + nivolumab 0.3 mg/kg	MVA 1 x 10  pfu + nivolumab 0.3 mg/kg

If a participant has a 0.5 log or greater drop in hepatitis B surface antigen at Day 35, they may receive a booster dose of MVA-HBV, at the Investigator's discretion and after discussion with the Sponsor (UK participants only).

### 5.2.1 Study Vaccines

All participants will receive two doses of study vaccine, with or without nivolumab, on Day 0 and Day 28. Both vaccinations will be given by intramuscular injection into the deltoid muscle, to the same, non-dominant arm in a participant, where possible. If a participant has a 0.5 log or greater drop in hepatitis B surface antigen at Day 35, they may receive a booster dose of MVA-HBV at Month 3, at the Investigator's discretion and after discussion with the Sponsor (UK participants only).

The ChAdOx1-HBV dose is 2.5 x 10^10 vp, based on the review of the two doses studied in study HBV001. This dose, or higher, of ChAdOx1-based vaccines has been safely used in hundreds of participants (see Investigator's Brochure), and thousands of people have been immunised with a ChAdOx1 COVID-19 vaccine at a dose of 5 x 10^10 vp.

The dose of MVA-HBV will be fixed at 1 x 10^8 pfu, as taken from historical data of previous studies. A 1.5 x 10^8 pfu MVA dose was used in nearly 2,000 healthy participants in influenza studies conducted by Oxford University and Vaccitech.

### 5.2.2 Nivolumab

Nivolumab will be administered via intravenous infusion over 30 minutes, following vaccination. The dose to be used in this study (0.3 mg/kg) is one tenth that commonly indicated for cancer immunotherapy. Full prescribing and safety information for nivolumab can be found in the SmPC or package Insert.

## 5.3 Labelling, Packaging and Shipping

The vials of study vaccine will be labelled according to local regulations.

Study vaccine will be shipped by the Contract Manufacturing Organisation (CMO) to the study centres on dry ice with a continuous temperature monitoring device. Nivolumab will also be provided and labelled for investigational use by the CMO.

Upon receipt, the pharmacist or designee must immediately inspect all vials for damage. Any damage or discrepancies from the packing list must be documented and promptly discussed with the Sponsor and the Study Monitor to determine the appropriate action. The temperature

monitors should be downloaded according to the accompanying instructions in the shipment. Temperature records must be sent to the Sponsor and the centre will receive written confirmation that the vials are clinically released before they are used. If the temperature monitor has been out of range, then the shipment should be placed into quarantine and the Sponsor and Study Monitor contacted immediately to determine whether the study vaccine may be used.

At the start of the study, a sufficient number of study vaccine vials will be shipped to each study centre based on projected recruitment at each centre with appropriate overage in case of spillage or breakage. Further study vaccine supplies may be requested following the re-supply process in the Pharmacy Manual.

#### **5.4 Storage**

Vials of ChAdOx1-HBV and MVA-HBV must be stored in a continuously monitored  $\leq -70^{\circ}\text{C}$  freezer and nivolumab must be stored in the outer carton (to protect from light) between  $2$  and  $8^{\circ}\text{C}$  in a continuously monitored refrigerator.

All study vaccine and study-labelled nivolumab must be kept in a secured location with no access for unauthorised personnel.

#### **5.5 Accountability**

The pharmacist or designee is required to maintain accurate accountability records for the study vaccine. Instructions and forms to be completed and kept for accountability will be provided to the pharmacist or designee. If the pharmacist or designee wishes to use study centre-specific accountability forms, these must be reviewed and approved in advance by the Sponsor. Upon completion of the study, all accountability records will be copied and the copies filed in the electronic Trial Master File (eTMF). The originals must be maintained at the study centre with the rest of the study records.

The number of vials of study vaccines and nivolumab received and dispensed must be recorded on a participant by participant basis, including the applicable batch number.

#### **5.6 Destruction or Disposal**

The Sponsor will provide instructions for the return of unused ChAdOx1-HBV and MVA-HBV vaccines and study-labelled nivolumab. Genetically modified organism (GMO) waste, including empty vials after full study vaccine accountability has been conducted, will be destroyed by appropriately licensed vendors. This destruction will be recorded with an original copy kept at the centre and a copy sent to the eTMF.

#### **5.7 Method of Assigning Participants to Treatment Groups**

Participants have so far been randomised to all open groups in a 1:1:1:1 allocation as each group is initiated. Protocol Version 6.0 closes Groups 1 and 4 to further randomisation and all remaining participants will be randomised to Groups 2 and 3 only in a 1:1 ratio.

A sentinel participant will be dosed in cohort 1, and the rest of the cohort will only be enrolled at least 48 hours later. Following the 7-day safety assessment of the first 6 participants in Group 1 by the SMC, Group 2 will be initiated. Groups 3 and 4 will be initiated after evaluation of safety data 7 days after the first 6 participants in Group 2 have received ChAdOx1-HBV. At the screening visit, participants will be sequentially allocated a screening number once written, informed consent has been obtained. They will be identified by this number until entry into study.

Participants fulfilling entry criteria will be allocated an enrolment number and allocated to treatment based on the treatment schedule prepared by statistician.

Once screening and enrolment numbers have been assigned, no attempt will be made to use those numbers again. If an enrolment number is allocated incorrectly, no attempt will be made to remedy the error once the study vaccine has been dispensed. Any participants that are withdrawn prior to either vaccination will be replaced on a case by case basis following discussion with the Sponsor. Discontinued participants following vaccination who do not complete all follow-up visits will be replaced following discussion with the Sponsor.

Any replacement participants will be given the next sequential participant number.

The treatment schedule list will be held by the statistician during the study.

## **5.8 Selection of Doses, Dosing Schedule and Administration**

### ***5.8.1 Selection of Doses in the Study***

The ChAdOx1-HBV dose is  $2.5 \times 10^{10}$  vp, based on the review of the two doses studied in study HBV001 ( $2.5 \times 10^9$  vp and  $2.5 \times 10^{10}$  vp). Safety data from all healthy volunteers was reviewed from HBV001 by the SMC, and the higher dose was chosen to use in this study. This dose, or higher, of ChAdOx1-based vaccines has been safely used in hundreds of participants (see Investigator's Brochure), and thousands of people have been immunised with a ChAdOx1 COVID-19 vaccine at a dose of  $5 \times 10^{10}$  vp. The dose of MVA-HBV will be fixed at  $1 \times 10^8$  pfu as taken from historical data of previous studies. A  $1.5 \times 10^8$  pfu MVA dose was used in nearly 2,000 healthy participants in influenza studies conducted by Oxford University and Vaccitech.

The dose of nivolumab will be fixed at 0.3 mg/kg to be given intravenously over 30 minutes.

### ***5.8.2 Selection and Timing of Dose for each Participant***

#### ***5.8.2.1 Dosing Schedule***

The participants will be allocated to dosing group depending on the treatment schedule and groups open at the time of randomisation. Vaccination will be performed on Day 0, after eligibility has been reconfirmed, and on Day 28.

If a participant has a 0.5 log or greater drop in hepatitis B surface antigen at Day 35, they may receive a booster dose of MVA-HBV at Month 3, at the Investigator's discretion and after discussion with the Sponsor (UK participants only).

There are no restrictions in the time of day that the vaccination should be administered or in timing of vaccination in relation to meals.

#### ***5.8.2.2 Study Vaccine Preparation and Administration***

ChAdOx1-HBV and MVA-HBV vials should be allowed to reach room temperature before use.

The study vaccines will be provided at  $1 \times 10^{11}$  vp/ml ChAdOx1-HBV and  $2 \times 10^8$  pfu/ml for MVA-HBV. The appropriate doses will be prepared by dilution of individual vials on a per participant basis by study staff according to the procedure in the Pharmacy Manual. Dose Preparation kits including equipment will be provided by the Sponsor.

Both vaccinations will be given by intramuscular injection into the deltoid muscle, to the same, non-dominant arm in a participant, where possible. All vaccinations will be made by a suitably

qualified health professional. A second study team member will perform a check of the vaccine dilution to ensure the right dilution is performed.

The suitably qualified healthcare professional will wear gloves, eye protection and an apron or laboratory coat/gown during the procedure. The vaccination site will be covered with a sterile dressing to minimise dissemination of the recombinant virus into the environment. This should absorb any virus that may leak out through the needle track. The sterile dressing will be removed approximately 10 minutes after vaccination. The dressing will be discarded as GMO waste. No further dressing coverage is needed.

Allergic reactions to vaccination are possible, therefore, appropriate drugs and medical equipment to treat acute anaphylactic reactions must be immediately available and a medically qualified study team member trained to recognise and treat anaphylaxis must be present in the clinic during the entire vaccination procedure and post-vaccination observation period.

#### *5.8.2.3 Nivolumab Preparation and Administration*

Nivolumab will be prepared according to the Pharmacy Manual.

In Groups 3 and 4, the patients will be observed for 30 minutes after vaccination. If there are no safety concerns (vital signs and reactogenicity), nivolumab will be infused over 30 minutes and the patients will be observed in the study centre for a further 30 minutes post-infusion.

#### *5.8.2.4 Dose and Schedule Modifications*

Every effort will be made to administer the planned doses of study vaccines and nivolumab.

### **5.9 Blinding**

This is an open label study; therefore, no procedures for blinding are necessary. The study team members and participant will know the treatment the participant is receiving.

### **5.10 Prior and Concomitant Vaccines and Medications**

Patients will have been taking antivirals for at least 12 months before screening. Once randomised to the study, oral antiviral medication should not be withdrawn. Patients should remain on the same dose of antivirals that they were on when they entered the study for the duration of the study.

Allowed antiviral medications include: entecavir, tenofovir (tenofovir alafenamide fumarate or tenofovir disoproxil fumarate), or besifovir.

Prior and concomitant medications include prescription and non-prescription drugs or other treatments, and any vaccines other than the study vaccine.

Recently used and ongoing medications will be reviewed and recorded during screening.

Concomitant medications used by participants post-vaccination will coincide with the collection period of adverse events. All medications taken to treat solicited AEs will be recorded in the eDiary and will be discussed with the participant at the scheduled clinic visits during the study. All medications taken to treat unsolicited AEs and SAEs will be recorded in the eCRF by questioning the participant at each visit whether they took any concomitant medications since the previous visit.

The name of the medication, treatment start and stop dates (or 'ongoing'), and indication must be recorded on the concomitant medication eCRF. The indication recorded on the concomitant medication eCRF must correspond to a medical term/diagnosis recorded on the adverse event

eCRF, or to a pre-existing condition noted in the participant's medical history, or be noted as prophylaxis, e.g. dietary supplement.

Also, participants should not receive any adenoviral-based vaccine within 3 months prior to or 3 months after administration of ChAdOx1-HBV on Day 0.

### **5.11 Treatment Compliance**

Vaccine administration will take place at the study centre and will be performed by a suitably qualified healthcare professional. The precise date and time of vaccination shall be documented in the source documents and eCRF. The study will be monitored by a Study Monitor approved by the Sponsor. During monitoring visits, all procedures will be monitored for compliance with the protocol. Source documents will be reviewed and compared with the data entries in the eCRFs to ensure consistency.

### **5.12 Post-study Treatment**

The Sponsor does not intend to provide ChAdOx1-HBV nor MVA-HBV after the end of the study or after any early participant withdrawal, as there is currently no clinical data supporting their efficacy. These participants will remain under the care of their healthcare professionals and treated according to standard care. If new information becomes available that would inform the benefit of repeat dosing, this will be considered as a protocol amendment at a later time.

## 6 STUDY PROCEDURES AT EACH VISIT/SCHEDULE OF ASSESSMENTS

The study consists of the following:

- A 42-day screening period before the start of study treatment
- A study period of 9 months
- An end of study visit

The schedule of assessments at each visit is shown in [Table 2](#) and listed in [Section 6.1](#) to [Section 6.3.1](#). The study assessments are described in [Section 7](#).

**Note: any additional visits or assessments performed during the study e.g. to assess adverse events must also be recorded on the unscheduled procedures or unscheduled visits in the eCRF.**

Unsolicited adverse events will be recorded from the date the informed consent is signed and at all clinic visits, by questioning the participant at each visit whether they had any adverse events since the previous visit and by observing the participant during clinic visits.

Serious adverse events and AESIs will be recorded from the date the informed consent is signed until the end of the study and/or resolved or until participant contact discontinues.

Solicited AEs and medication taken to treat solicited AEs will be collected daily in the eDiary for 7 days post-vaccination.

All medications taken to treat unsolicited AEs and SAEs will be recorded in the eCRF by questioning the participant at each visit whether they took any concomitant medications since the previous visit.

Due to the COVID-19 pandemic, study centres will follow any local procedures in line with testing to ensure the safety of participants and staff.

### 6.1 Screening and Baseline Assessments

Written informed consent for participation in the study must be obtained before performing any study specific screening tests or evaluations according to the process in [Section 13.4](#).

The following will be performed at screening:

- Demographic data will be collected
- Height and weight will be measured
- A medical and disease history will be recorded, including any medications being taken
- A blood sample will be taken for HIV, HCV, HBV (quantitative HBV DNA and quantitative HBsAg), HDV diagnostic testing
- A urinalysis dipstick test will be performed
- A urine drug screen will be performed
- A urine pregnancy test will be performed, childbearing status recorded and if of childbearing potential, assessment of contraceptive measures performed
- Blood samples will be taken for haematology (including prothrombin time [PT] and INR), biochemistry and liver function tests (LFTs)
- A full physical examination will be performed
- Vital signs (pulse rate, blood pressure and temperature) will be measured

**Table 2 Overall Schedule of Assessments at Each Study Visit**

Visit/Call	Screen	Vaccination Clinic	Telephone Call	Clinic	Vaccination Clinic	Telephone Call	Clinic			End of Study / Early Discontinuation Clinic
Timepoint (window)	Day						Month			
	-42 to -1	0	1 (+1d)	7 (±1d)	28 (+2d)	29 (+1d)	35 (±1d)	3 (±7d)	6 (±7d)	9 (±7d)
Informed consent	X									
Baseline/eligibility variables										
Demographics	X									
Inclusion and exclusion criteria	X									
Height and weight	X									
Medical and disease history	X									
HIV, HCV, HBV (quantitative HBV DNA and quantitative HBsAg), HDV serology	X									
Urinalysis	X									
Urine drug screen	X									
Urine pregnancy test (β-hCG)	X	X [a]			X [a]			X [f]	X [f]	X
Laboratory eligibility and safety tests										
Haematology	X	X [a]		X	X [a]		X	X	X	X
Biochemistry	X	X [a]		X	X [a]		X	X	X	X
Liver function tests	X	X [a]		X	X [a]		X	X	X	X
Study vaccination										
Vaccination dose		X			X			X [g]		
Post-dose observation		X			X			X [g]		
Nivolumab dose (Group 3 only) [b]					X					
Other safety assessments										
Full physical examination	X	X [a]			X [a]			X [a]		X
Symptom-directed physical examination				X			X	X	X	
Vital signs	X	X		X	X		X	X	X	X
Local/systemic reactogenicity		X [c]	X	X	X [c]	X	X	X [c]		
Unsolicited adverse events [d]	X	X	X	X	X	X	X	X	X	X
Serious adverse events and adverse events of special interest	X	X	X	X	X	X	X	X	X	X
Prior and concomitant medications	X	X	X	X	X	X	X	X	X	X
Blood for HBV disease markers [e]		X [a]		X	X [a]		X	X	X	X
Immunogenicity assessments										
Blood for cellular immunogenicity assessments		X [a]		X	X [a]		X	X [a]	X	X

[a] Pre-vaccination on Day 0, Day 28, and Month 3 (for UK participants having an MVA-HBV boost)

[b] Participants in Group 3 will receive nivolumab on Day 28. Group 4 is now closed. The patients will be observed for 30 minutes after vaccination. If there are no safety concerns (vital signs and reactogenicity), nivolumab will be infused over 30 minutes and the patients will be observed in the study centre for a further 30 minutes post-infusion.

[c] Captured pre-vaccination and post-vaccination on Days 0 and 28, and Month 3 (for UK participants having an MVA-HBV boost), via eDiaries for 7 days post-vaccination and then at the clinic assessment 7 days post-vaccination (Day 7 or 35)

[d] Recorded in the eCRF from the date the informed consent is signed, at all clinic visits to cover the period since the previous visit and during the visit

[e] Individual disease markers tested according to the Study Laboratory Manual

- [f] Pregnancy testing at Month 3 in Groups 1 and 2 if an MVA-HBV boost is given, and at Months 3 and 6 in Groups 3 and 4
- [g] If a participant has a 0.5 log or greater drop in hepatitis B surface antigen at Day 35, they may receive a booster dose of MVA-HBV at Month 3, at the Investigator's discretion and after discussion with the Sponsor (UK participants only). These patients will also have a telephone call the day after the boost vaccination and a clinic visit 7 days post-boost, as per Day 1 and Day 7.

All screening evaluations must be completed and reviewed to confirm that participants meet all eligibility criteria before the first dose of study vaccine. The Investigator will maintain a screening log to record details of all participants screened and to confirm eligibility or record reasons for screening failure, as applicable.

Participants who do not meet eligibility criteria may be rescreened at the discretion of the Investigator. Only abnormal/ out of window tests are required to determine eligibility. Re-screening can occur at any point with the allowed overall screening window (up to 42 days).

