**Figure 2 Overall Study Design**

Abbreviations: ChAdOx1=chimpanzee adenovirus vector; HBV=hepatitis B virus; MVA=modified vaccinia virus Ankara; pfu=plaque forming units; vp=viral particles

Greyed Groups = closed

All treatment groups will receive study vaccine on Day 0 and Day 28. In Group 1, MVA-HBV will be evaluated 7 days after the first dose of study vaccine in the first 6 participants prior to initiation of the prime-boost regimen of ChAdOx1-HBV followed by MVA-HBV (Group 2). Participants in Groups 3 and 4 will be dosed in parallel to receive ChAdOx1-HBV (with and without nivolumab) on Day 0 followed by MVA-HBV with nivolumab on Day 28. Groups 3 and 4 will be initiated after evaluation of data 7 days after the first 6 participants in Group 2 have received ChAdOx1-HBV. The evaluations will be carried out by a Safety Monitoring Committee (SMC) consisting of the Sponsor Medical Monitor, the Country Lead Investigators for South Korea, Taiwan and the UK, and the trial Medical Monitor. If a participant has a 0.5 log or greater drop in hepatitis B surface antigen at Day 35, they may receive a booster dose of MVA-HBV, at the Investigator's discretion and after discussion with the Sponsor (UK participants only).

A Data Monitoring Committee (DMC) composed of three independent experts (two clinicians and one statistician) will be appointed to perform unscheduled reviews of the available safety and tolerability study data and make recommendations concerning the continuation, modification or termination of the study if one of the study stopping or holding rules defined in [Section 3.1.3](#) is met.

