### ***3.1.3 Stopping Criteria/Holding Criteria***

There will be a review of the study data by the DMC when there is a reasonable possibility that the investigational vaccine caused any of the SAEs or severe adverse events listed below, based on the assessment of the Investigator, in one or more participants at any dose. Vaccinations will be put on hold pending this review:

- Death related to study vaccine
- Life-threatening adverse event or life-threatening suspected reaction
- Serious suspected adverse reaction
- Suspected unexpected serious adverse reaction (SUSAR)
- Acute allergic reaction or anaphylactic shock following the administration of vaccine investigational product
- Anaphylaxis or bronchospasm, indicative of an immediate hypersensitivity reaction to study vaccine
- If any participant has any of the following during the study:
  - Alanine aminotransferase (ALT) or aspartate aminotransferase (AST) >3 x upper limit of normal (ULN) and total bilirubin >2 x ULN or International Normalised Ratio (INR) >1.5
  - ALT or AST >3 x ULN with the appearance of fatigue, nausea, vomiting, right upper quadrant pain or tenderness, fever, rash, and/or eosinophilia (>5%)
  - Grade 4 diarrhoea, hypothyroidism, hyperthyroidism, hypophysitis, adrenal insufficiency, rash, toxic epidermal necrolysis, Stevens-Johnson syndrome, diabetes, other immune-related adverse reaction, or creatinine elevation
  - Grade 3 myocarditis or pneumonitis
  - Solicited local adverse events: If three out of the first 20 participants dosed with a study vaccine, or >10% of participants, thereafter, are followed by the same Grade 3 solicited local adverse event

- Solicited systemic adverse events: If three out of the first 20 participants dosed with a study vaccine, or >10% of participants, thereafter, are followed by the same Grade 3 solicited systemic adverse event
- Unsolicited adverse events: If three participants of the first 20 participants dosed, or >10% of participants, thereafter, develop a Grade 3 unsolicited adverse event of the same type that is considered related to study vaccine

Other potential reasons for discontinuation of the second planned dose of nivolumab for Group 4 are found in [Appendix 2 – Toxicity Management Guidelines for Nivolumab](#).

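### The Version 6.0 visit schedule limits the nivolumab row to Group 3, while the dosing text still plans Day 28 nivolumab for participants already randomised to Group 4

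*Protocol*

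**What the plan says.** Protocol Table 2 has one nivolumab row, labelled "Nivolumab dose (Group 3 only) [b", with a single mark at Day 28. Note [b] gives the context: "Participants in Group 3 will receive nivolumab on Day 28. Group 4 is now closed". It does not say to what Group 4 is closed.

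The body text does. Section 5.2 states "Groups 1 and 4 are closed to further randomization", and Section 5.7 states "Protocol Version 6.0 closes Groups 1 and 4 to further randomisation". Sections 3.1.1 and 4.1 say the same in substance. No section says that participants already in Group 4 stop study treatment.

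Other current sections keep nivolumab for Group 4:

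- Table 1 lists the Group 4 Day 28 treatment as MVA "pfu + nivolumab 0.3 mg/kg", the same entry as for Group 3.
- Section 3.1.1: "Participants in Groups 3 and 4 will be dosed in parallel", with ChAdOx1-HBV "on Day 0 followed by MVA-HBV with nivolumab on Day 28".
- Section 3.1.3 refers to reasons for "discontinuation of the second planned dose of nivolumab for Group 4", so that dose is still treated as planned.
- Section 5.8.2.3 gives the infusion and observation procedure for Groups 3 and 4 together.
- Section 5.8.2.4 asks sites to make every effort to give the planned vaccine and nivolumab doses.
- Section 6.2, on treatment-day procedures, refers to Table 1 for nivolumab.

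**The concern.** A site that plans a Day 28 visit from Table 2 finds no nivolumab entry for Group 4. A site that plans the same visit from Table 1 finds one. Both are current Version 6.0 text, and both concern an investigational infusion on a treatment day.

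The omission at Day 0 does no harm, because nobody is newly randomised to Group 4 under Version 6.0. The conflict concerns only participants already in Group 4 with the Day 28 dose outstanding.

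What is at stake for the analysis is limited but real. Under Table 1 the groups receive nivolumab never (Groups 1 and 2), at Day 28 only (Group 3), or at Days 0 and 28 (Group 4). A Group 4 participant without the Day 28 infusion would have received nivolumab at Day 0 only, which is not the planned regimen of any group. One secondary objective concerns the timing of PD-1 blockade relative to vaccination, and Groups 3 and 4 are the arms that differ in that timing.

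**Working it through.** The plan states no figure to reproduce. The check has three parts: a comparison of text, a bound on the number exposed, and a trace through the analysis sets.

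**1. Text comparison for a Group 4 participant at Day 28**

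| Source (Protocol) | Nivolumab at Day 28 for Group 4? |
|---|---|
| Table 2 row label | No; Group 3 is the only group named |
| Table 2 note [b] | Not mentioned; the group is described as closed |
| Table 1 | Yes |
| Section 3.1.1 | Yes |
| Section 3.1.3 | Second dose treated as planned |
| Section 5.8.2.3 | Infusion procedure covers Group 4 |
| Section 6.2 | Refers to Table 1 |

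No section says which table takes precedence.

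**2. How many participants could be exposed**

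Inputs:
- Group 4 participants with Month 3 data at the review behind Version 6.0: 6 (Section 3.2).
- Group 4 size: 8 to 10 (Protocol Table 1); 9 at the end of enrolment (SAP 8.1).
- Day 28 window: +2 days (Table 2). A contraindicated vaccination may be given up to 28 days after its scheduled time (Section 4.3.1.1).
- Month 3: Day 91 ± 7 (SAP Table 3).

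The 6 reviewed participants were past the second dose. The latest permitted delayed dose is Day 28 + 28 = Day 56, and the earliest Month 3 visit in window is Day 91 − 7 = Day 84.

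The remainder:
- using the protocol range: 8 − 6 = 2 to 10 − 6 = 4;
- using the SAP final count: 9 − 6 = 3.

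These are ceilings. They count Group 4 participants without reviewed Month 3 data, not participants between doses. The exposed interval is Day 0 to Day 30, or to about Day 56 with a delay, so someone not yet at Month 3 could already have had the second dose. No dosing dates are given. The number affected is therefore 0 to 4, and cannot be narrowed from the documents.

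**3. Where an omitted infusion would go in the analysis**

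- Intent-to-treat set (SAP 9.2.2): presented by randomised group, so the participant stays in Group 4.
- Per-protocol set (SAP 9.2.4): requires the correct study vaccine at both vaccinations and no major deviation that could bias the analyses. A missed nivolumab infusion is not named as an exclusion, but the deviation review could make it one.
- Immunogenicity set (SAP 9.2.5): drawn from the per-protocol set and presented by randomised group. The participant stays in Group 4 unless excluded for a major deviation.
- Safety set (SAP 9.2.3 and SAP Table 2): a Group 4 participant whose second nivolumab dose was not given remains in Group 4.

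**The case against.** The strongest reply is that the dosing text is consistent and only a row label is out of step. Section 6.2 sends the reader to Table 1 for nivolumab, Section 5.8.2.4 asks for planned doses to be given, and Table 2 is a schedule of assessments. Note [b] does not say that Group 4 stops nivolumab. Since Version 6.0 randomises only to Groups 2 and 3, the row can be read as describing new recruits. Nothing in the documents shows that any Group 4 infusion was omitted because of Table 2, and SAP 12.5 would tabulate the reason for any missed nivolumab dose by vaccination day.

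Most of this stands, and it is why the point is small. Two parts do not settle it. The reference in Section 6.2 is not a precedence rule, and Section 6 presents Table 2 as the schedule at each visit without limiting it to new recruits. The new-recruits reading also sits badly with note [f] of the same table, which still sets pregnancy tests for Groups 1 and 4, both closed. As it stands, Table 2 covers participants in closed groups but has no nivolumab entry for Group 4.

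**Conclusion.** The inconsistency is in the current Version 6.0 text. Its severity is minor. It affects only Group 4 participants between Day 0 and Day 28 when Version 6.0 took effect at their site, which is 0 to 4 people and possibly none. The upper bound assumes that the 6 reviewed Group 4 participants had all reached Month 3, and that Group 4 finished within the stated 8 to 10.

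A reader might infer three stronger things that the documents do not support:

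- **That Version 6.0 withdrew the second infusion from Group 4.** Closure is defined only as closure to further randomisation, and no section withdraws the dose.
- **That about a third of Group 4 was affected.** 3/9 = 33% (or 2/8 = 25% to 4/10 = 40% over the planned range) is the share without reviewed Month 3 data. It is a ceiling, not an estimate.
- **That SAP Table 2 would mix regimens in the PD-1 timing comparison.** That table assigns groups for the safety analysis only. The timing objective concerns immunogenicity, where grouping follows randomisation. Keeping a participant in the randomised group is ordinary intent-to-treat practice, and the deviation review can act on the per-protocol and immunogenicity sets.

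**What to change.** Reconcile the Table 2 nivolumab row label and note [b] with Table 1 and Sections 3.1.1, 3.1.3, 5.8.2.3 and 6.2. Add one sentence stating what closure means for the treatment of participants already randomised to Group 4. Which instruction applies is the sponsor's decision, and this review takes no position on it.

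The cost is a short clarification to one row label and one note. No change to sample size or analysis follows. If all Group 4 participants had passed Day 28 by the time Version 6.0 took effect, a statement to that effect would settle the practical question.
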